9.1.4 Treatment Week 56, End of Study; Early Termination (Visit 16)

The end of study visit will be performed for subjects completing the study or for subjects who are withdrawn from the study prior to completion of the study at the time of their treatment termination. For subjects who withdraw from the study prior to completion, the site will also attempt to contact the subject at or about the 56-week time point to obtain end of study assessments.

Activities at the end of study visit include:

- Administer PHQ-9, C-SSRS, and IWQOL-Kids questionnaires;
- Administer neurocognitive battery (CANTAB);
- Obtain vital signs;
- Obtain weight and waist circumference measurements;
- Measure height and calculate BMI;
- Collect study drug from previous visit, assess treatment compliance, and perform drug accountability;
- Obtain blood sample for chemistry, hematology, and lipids, panel;
- Obtain blood sample for HbA1c;
- Obtain urine sample for routine urinalysis and urine pregnancy test (female only);
- Administer glucose load for OGTT and obtain blood sample for glucose and insulin at 2 hours following oral glucose load (Section 10.10);
- Perform complete physical examination (include Tanner Staging);
- Perform and evaluate 12-lead electrocardiogram (ECG);
- Conduct hand and wrist X-ray;
- Conduct DXA measurement (if applicable);
- Record any changes in concomitant medications;
- Record any adverse events reported or observed;
- Discontinue subject's study participation.

9.2 Study Period

The study period for each subject will begin when written informed consent is provided and will continue until Week 56 or early termination is completed. Sites should link the scheduling of visits to the baseline/randomization visit (Visit 2, Day 0). Visit windows are provided to allow subject and site scheduling convenience. However, every effort should be made to ensure that visits occur within these windows so that the overall treatment duration is 56 weeks for subjects

who complete all visits. In certain instances, adverse event information may be required for events occurring after the study period (Section 11.3).

10.0 ASSESSMENT

[figure not shown]
10.1 Weight Measurement

Subject weight will be obtained at every study visit. Subjects should be weighed using a calibrated scale. The same scale should be used for each measurement, and measurements should be evaluated by the same site personnel at each visit, whenever possible. Subject weights should be obtained, whenever possible, under the same conditions (no shoes, clothing of similar weight) that were employed at the first (Screening) weigh-in. Subjects should be encouraged to complete their weigh-in visits in the morning.

10.2 Waist Circumference Measurement

Waist circumference measurements will be taken using a measuring tape provided by the sponsor or designee, and should be obtained by the same individual, whenever possible, at every study visit. To measure the waist circumference, locate the top of the right iliac crest. Place the measuring tape in a horizontal plane (parallel to the floor) around the abdomen at the level of the top of the iliac crest as shown in Figure 2.

Figure 2. Measuring Tape Position for Waist Circumference Assessments

Ensure that the subject is relaxed. Ensure that the tape is snug but does not indent or compress the skin, and make the measurement (in centimeters) at the end of a normal expiration.

10.3 Height and BMI

Height measurements (cm) and BMI will be determined by the site at every visit (see BMI Chart in [Appendix 2](#)). Height measurements should be made using a calibrated stadiometer without shoes, socks, or hats. At each study visit, 3 independent measurements of height should be made, and the median value from these measurements recorded on the eCRF. Height should be recorded to the nearest centimeter. The same stadiometer should be used for all visits for any given subject. Stadiometer should be calibrated, at least daily, if used, following the equipment's manufacturer instructions and/or site SOP.

If a subject does not meet the BMI criterion for inclusion into the study (see CDC Clinical Growth Chart⁸ in [Appendix 3](#)), no further screening procedures should be undertaken.

10.4 Vital Signs

Vital signs (systolic blood pressure, diastolic blood pressure, heart rate, respiration rate, temperature) will be assessed at each study visit. Subjects should be seated comfortably for at least 10 minutes prior to assessing vital signs. Heart rate and respiratory rate measurements should be made by counting events (heartbeats or breaths) for a period of 30 seconds and multiplying these values by 2 to obtain the rates per minute. A calibrated cuff should be employed for blood pressure measurements. Site staff should ensure at the Screening visit that the cuff size used is appropriate for the patient's arm circumference. Overweight and obese subjects often require a larger cuff than is typically used for adults of normal size and weight. The same cuff should be used for the same subject across multiple visits when blood pressure is performed. The same person should perform all assessments for a given subject.

10.5 Physical Examinations and Tanner Staging

A complete physical examination will be performed at baseline, and end of study or early termination visits. The physical examination will consist of an examination of the following systems: general appearance, skin, eyes, ears, nose, throat, neck (including thyroid), lymph nodes, chest, heart (including any auscultated cardiac murmurs), abdomen, extremities, and neurologic. Puberty maturation will be assessed using the Tanner Staging (also known as the Sexual Maturity Rating (SMR), a gender specific 5-point scale of secondary sexual characteristics. Boys are rated for genital development and pubic hair growth, and girls are rated for breast development and pubic hair growth. Tanner Staging should be conducted by site personnel who have been trained on the proper technique for these assessments, and sites should ensure that the same observer conducts all Tanner Staging evaluations for any given subject.

10.6 Electrocardiograms

Twelve-lead ECG studies will be performed at baseline, and end of study or early termination visits. ECGs will be evaluated for clinically significant abnormalities that would prevent entry into the study, and for arrhythmias, conduction disturbances, or other clinically relevant changes between randomization and each of the subsequent evaluations. Parameters including heart rate, R-R, P-R, QT intervals, and QRS duration will be recorded.

10.7 X-Ray of the Hand and Wrist

An X-ray of the hand and wrist will be performed at baseline, and end of study or early termination visit to assess bone growth. Equipment and procedures used to obtain hand and wrist X-ray data will be standardized as described in a separate document. X-rays will be read at a central facility and the reader will be blinded.

10.8 DXA (Sub Study)

A bone health sub-study will be conducted at selected sites in approximately 100 subjects (25 each on placebo and mid-dose, and 50 on top-dose) to assess the effect of Qsymia administration on bone health using Dual X-ray Absorptiometry (DXA). DXA scans of the posterior-anterior (PA) spine (lumbar), and total body less head (TBLH) will be performed at baseline and at the end of study or early termination. Equipment and procedures used to obtain DXA data will be standardized as described in a separate document. Sites involved in DXA measurement will be trained on these procedures prior to performing scans on study subjects. Scans will be read at a central facility and the reader will be blinded.

The following enrollment criteria will apply:

- 1) Both male and female will be eligible to participate;
- 2) Subjects with a history of any non-traumatic fracture will not be eligible;
- 3) Subjects with juvenile osteoporosis at baseline will not be eligible; and
- 4) Subjects must meet manufacturer equipment specifications with regard to height and weight limitations.

10.9 Laboratory Tests

Laboratory tests will be performed at a licensed, certified central testing laboratory identified by the sponsor. Laboratory tests will be used to determine eligibility for study participation, for safety monitoring and to determine which subjects may progress to later phases of the study.

Subjects should be fasting for at least 8 hours prior to obtaining blood samples for analyses. Table 2 summarizes the clinical laboratory testing for the study. Laboratory tests required at each study visit are detailed in Section 9.0 and [Appendix 1](#).

Table 2: Clinical Laboratory Tests

Fasting blood chemistry	Hematology	Other

 • albumin • alkaline phosphatase • ALT • AST • GGT • bicarbonate • blood urea nitrogen • serum calcium • serum chloride • serum sodium • carbon dioxide • creatinine (and estimated creatinine clearance) • glucose • lactate dehydrogenase • serum phosphorus • serum potassium • total and direct bilirubin • total protein • uric acid 	
 • hemoglobin • hematocrit • red blood cell count • red blood cell indices • total white blood cell count • white blood cell differential (neutrophils, lymphocytes, monocytes, eosinophils, and basophils) • platelet count 	
 • thyroid stimulating hormone
		Urinalysis
		
 • midstream urinalysis with reflex microscopic evaluation • pregnancy test (all female subjects)
		Urine Drug Screen
		
 • cannabinoids • amphetamines • cocaine • barbiturates • benzodiazepine • opiates
	Lipid panel	
	
 • total cholesterol • LDL-C • HDL-C • triglycerides 	
	Glycemic testing	Serology
	
 • HbA1c • insulin • glucose 	
 • HBsAg • HCV • HIV

10.10 Oral Glucose Tolerance Test

An oral glucose tolerance test (OGTT) will be obtained at baseline (after results from screening visit indicate the subject may be eligible for participation), and at end of study or early termination for all subjects.

The OGTT will use a 75 g oral glucose load; blood samples will be obtained at baseline and at 2 hours post glucose load for evaluation of both glucose and insulin levels.

10.11 CANTAB (Cambridge Neuropsychological Test Automated Battery)

Cognitive function will be assessed using selected tests from the CANTAB including paired associates learning, pattern recognition memory, and spatial span. The CANTAB will be assessed at screening (familiarization session only), baseline, Week 16 (Visit 6), and end of study or early termination.

10.12 IWQOL-Kids

The Impact of Weight on Quality of Life-Kids (IWQOL-Kids) questionnaire ([Appendix 6](#)) is a 27-item, self-administered instrument that will be completed at baseline, and end of study or early termination.

The IWQOL-Kids is validated for use in adolescents aged 11-19 years old. This questionnaire is designed to evaluate the impact of excess weight on quality of life domains including physical mobility and comfort (Physical Comfort), how an individual feels about themselves and their body (Body Esteem), how an individual is treated in their social environment (Social Life), and the individual's perception of what family members may think and feel about them (Family

Relations).⁹ Because this instrument is intended to be completed directly by study subjects, it is important that site personnel remain neutral and do not influence subject answers on this questionnaire in any way. Should subjects ask questions to site personnel regarding the meaning of specific items, site personnel should not interpret items for the subjects, rather, they should repeat items back to subjects as they are worded on the instrument.

Site personnel must also recognize that the subject's answers to this questionnaire reflect their perceptions and attitudes at the time the questionnaire is completed, and that missing answers cannot be queried at a later date. It is critical, therefore, that site personnel review questionnaires for completeness at the time they are initially filled out, and that any missing answers are completed before the subject leaves the office.

10.13 PHQ-9: Modified for Teens

The Patient Health Questionnaire for Adolescents (PHQ-9: Modified for Teens) ([Appendix 4](#)) is a 9-item, self-administered instrument for the assessment of depression in adolescents.

Because this instrument is intended to be completed directly by study subjects, it is important that site personnel remain neutral and do not influence subject answers on this questionnaire in any way. Should subjects ask questions to site personnel regarding the meaning of specific items, site personnel should not interpret items for subjects, rather, they should repeat items back to subjects as they are worded on the instrument. Because this questionnaire assesses the subject's level of depression over a specific time frame (the past 2 weeks), answers not completed by subjects at a given visit cannot be queried or filled in at a later date. Site personnel, therefore, must carefully review questionnaires for completeness before subjects leave the clinic, and assure that questionnaires are properly completed.

The PHQ-9 questionnaire is being used to screen for and to assess the severity of any depression in study subjects. This questionnaire will be completed at every visit. Answers to the questionnaire may reveal evidence of significant depression, including the possibility of suicidal thoughts or plans. It is the responsibility of the investigator to evaluate subjects' responses to these questionnaires carefully, and to perform any additional evaluation and management that is indicated, including referral to a mental health professional if necessary. The evaluation by the investigator will be guided by the standardized methods for the PHQ-9 that have been developed to provide information regarding diagnosis of depression, severity of symptoms, and treatment follow-up options. Investigators should document any such problems identified in study source documents using standard diagnostic criteria and terminology as provided in the standardized guidelines. It is expected that any randomized subject presenting with a PHQ-9 score of 15 or more should be treated and may require referral to a qualified mental health care professional.

10.14 Columbia Suicide Severity Rating Scale (C-SSRS)

The Columbia Suicide Severity Rating Scale is an 11-item clinician-administered assessment of both suicidal behavior (6 items) and suicidal ideation (5 items).¹⁰ Each of the items comprising this scale corresponds to a specific level, or severity of ideation or behavior, and is answered on a yes/no basis. This assessment will be administered to all subjects at screening in order to confirm the absence of suicidal behavior or ideation with at least some intent to act on it, and to document the pre-study status of all subjects included in the treatment program. Subsequently,

C-SSRS evaluations may be done at the investigator's discretion to evaluate and aid in diagnosis of reported or suspected events of suicidality. All C-SSRS assessments must be administered by a trained staff member. If any test reveals suicidal behavior or ideation with some intent to act on it, then test results must be confirmed by a physician investigator prior to discharging the subject from the study visit (see [Appendix 5](#)).

11.0 ADVERSE EVENT REPORTING

11.1 Adverse Events

Adverse events are defined as any untoward medical occurrences in subjects administered the study treatment, whether or not they have a causal relationship to the treatment. All observed or volunteered adverse events regardless of suspected causal relationship to the investigational product must be reported as described in the following sections.

Investigator must pursue and obtain information adequate to describe adverse events, their severity and relationship to study treatment, and their outcomes. For adverse events with a causal relationship to the investigational product, follow-up by the investigator is required for up to 28 calendar days after the last dose of study drug or until the events or their sequelae resolve or stabilize at a level acceptable to the investigator, and VIVUS concurs with that assessment. Investigators must also assess whether adverse events meet the criteria for classification as serious adverse events requiring immediate notification to VIVUS or its designated representative.

11.1.1 Severity Assessment

Investigators will assess the severity of all adverse events using the adjectives MILD, MODERATE, or SEVERE to describe the maximum intensity of each adverse event. For purposes of consistency, these intensity grades are defined as follows:

- MILD: Does not interfere with the subject's usual function;
- MODERATE: Interferes to some extent with the subject's usual function; or
- SEVERE: Interferes significantly with the subject's usual function.

Note the distinction between the severity and the seriousness of an adverse event. A severe event is not necessarily a serious event. For example, a headache may be severe (interferes significantly with subject's daily function) but would not be classified as serious unless it met one of the criteria for SAEs listed in Section 11.1.5.

11.1.2 Causality Assessment

Investigators are required to provide an assessment of causality for all adverse events (serious and non-serious) observed during this study. This assessment will provide a determination of whether, in the investigator's judgment, there exists a reasonable possibility that the investigational product caused or contributed to an adverse event. For this assessment, investigators must categorize the causality as either "related" or "not related". For an adverse event to be considered "related" to the study treatment, there should be evidence that the event follows a reasonable temporal sequence from the administration of study treatment, or that the

event follows a known response pattern to the drug. Causality would be further confirmed by improvement in an adverse event upon stopping the study treatment and reappearance of the event upon rechallenge.

11.1.3 Abnormal Test Findings

Merely repeating an abnormal test, in the absence of any of the above conditions, does not constitute an adverse event. Any abnormal test result that is determined to be an error does not require reporting as an adverse event.

The criteria for determining whether an abnormal objective test finding should be reported as an adverse event are as follows:

- Test result is associated with accompanying symptoms;
- Test result requires additional diagnostic testing or medical/surgical intervention;
- Test result leads to a change in study dosing or discontinuation from the study, significant additional concomitant drug treatment, or other therapy; or
- Test result is considered by the investigator or sponsor to represent a clinically significant finding.

11.1.4 Mood or Depression Related Events

All subjects will be screened for the presence and severity of depression at screening using a validated survey instrument (PHQ-9) designed for assessment of depression in a primary care setting. The PHQ-9 is a self-administered, nine-item depression module based directly on the diagnostic criteria for major depressive disorder in DSM-V-TR. This questionnaire may be used at the investigator's discretion at other times during the study to aid in diagnosis and evaluation of reported or suspected events of depression.

Suicidality will also be assessed at each study visit using the C-SSRS (see [Appendix 5](#)). The C-SSRS may also be used at the investigator's discretion at unscheduled visits during the study to aid in evaluation and diagnosis of reported or suspected events of suicidality. Should this additional assessment indicate the presence any suicidal behavior, or suicidal ideation with any intent to act on it, study treatment will be stopped, and the investigator must provide appropriate referral to a mental health professional for additional assessment and management. Any such event must be reported to the Medical Monitor and to the sponsor within 24 hours. Subjects must be followed until resolution of these events.

Any mood- or depression-related adverse events must be documented using standard diagnostic criteria and terminology.

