6.4 Safety Endpoints

Safety will be assessed by evaluation adverse events (AEs)/serious adverse events (SAEs); vital signs, laboratory parameters (screening, periodically during the study and end of study); electrocardiograms; physical examinations; cognitive function tests using the Cambridge Neuropsychological Test Automated Battery (CANTAB). All subjects will be screened for the presence and severity of depression using the PHQ-9: Modified for Teens ([Appendix 4](#)) and for suicidal/ideation using the Columbia Suicide Severity Rating Scale (C-SSRS) ([Appendix 5](#): Sample Columbia Suicide Severity Rating Scale) and follow up assessments will be done at each visit after treatment has been initiated. Bone age (X-ray of the hand and wrist) will be evaluated at baseline and end of study or early termination. Effect on bone mineral density and bone mineral content, as evaluated by Dual-energy X-Ray Absorptiometry (DXA) will be performed at baseline, end of study or early termination, at selected sites.

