9.1.2 Baseline/Randomization (Visit 2, Week 0)

Subjects eligible for treatment will be randomized and have study drug dispensed at visit 2. If a subject is found to be ineligible for participation due to laboratory values, the subject may be notified prior to visit 2. Activities at baseline are:

- Confirm inclusion/exclusion criteria (Section 7.0);
- Administer PHQ-9, C-SSRS, and IWQOL-Kids questionnaires;
- Administer neurocognitive battery (CANTAB);
- Obtain vital signs (blood pressure, heart rate, respiration rate, and temperature);

- Obtain weight and waist circumference measurements;
- Measure height and calculate BMI;
- Record any changes in concomitant medications;
- Record any adverse events reported or observed;
- Perform complete physical examination (include Tanner Staging);
- Perform and evaluate 12-lead ECG;
- Perform urine pregnancy test (female only);
- Perform OGTT for all subjects eligible for participation by results of Visit 1 screening tests (a separate visit may be scheduled for the OGTT) and obtain blood sample for glucose and insulin at 2 hours following oral glucose load;
- Conduct hand and wrist X-ray;
- Conduct DXA measurement (if applicable);
- Contact IWRS to randomize the subject. Dispense study drug and instruct the subject on the proper use of the study drug (Section 8.4.3);
- Provide diet (a 500-calorie/day deficit)/lifestyle modification and contraception/pregnancy counseling (female subjects); and
- Schedule the next study visit in 4 weeks (\pm 7 days).

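### The trigger for the suicidality drug stop and referral in Protocol 11.1.4 can be read as leaving out the scheduled C-SSRS tests, and 10.14 describes testing after screening as discretionary

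*Protocol*

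**What the plan says.** Protocol 11.1.4 deals with the PHQ-9 in its first paragraph and with suicidality in its second. The second paragraph runs in this order:

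- The scheduled test: "Suicidality will also be assessed at each study visit using the C-SSRS".
- The optional test: "The C-SSRS may also be used at the investigator's discretion at unscheduled visits during the study".
- The action rule: "Should this additional assessment indicate the presence any suicidal behavior, or suicidal ideation with any intent to act on it, study treatment will be stopped". The rest of that sentence makes referral to a mental health professional mandatory.
- The report: "Any such event must be reported to the Medical Monitor and to the sponsor within 24 hours".

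Protocol 10.14, which describes the instrument, requires the C-SSRS at screening and then says that "C-SSRS evaluations may be done at the investigator's discretion to evaluate and aid in diagnosis of reported or suspected events of suicidality". For any test showing suicidal behavior, or ideation with some intent to act, it says that "test results must be confirmed by a physician investigator prior to discharging the subject from the study visit".

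Elsewhere the C-SSRS is a scheduled procedure. Protocol 6.4 says "follow up assessments will be done at each visit after treatment has been initiated". Section 9.1.2 lists it at baseline ("Administer PHQ-9, C-SSRS, and IWQOL-Kids questionnaires"), 9.1.3 at Visits 3 to 15 and 9.1.4 at Visit 16. Appendix 1 marks it at all 16 visits. SAP 6.7.3 tabulates each item at each study visit.

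**The concern.** Two places leave a site in doubt about what to do with the C-SSRS after treatment starts.

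The first is the trigger in 11.1.4, *this additional assessment*. The nearest earlier assessment it can refer to is the optional one at unscheduled visits. On that reading, the drug stop and referral follow an optional C-SSRS but not the scheduled one.

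The second is 10.14. A site would look there for how to run the test, yet it describes testing after screening as discretionary and never states the every-visit requirement.

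What is at stake is uniform handling of a grave event in adolescents. With the same positive scheduled result, one site could stop drug and refer at once, while another confirms the result and then decides case by case. Safety is a primary objective of this trial.

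**Working it through.** The plan states no figure on this point. The check sets the sections side by side and then counts visits.

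**Step 1: what the trigger can refer to.** Two readings of 11.1.4 are possible.

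- *Broad:* the C-SSRS as a whole, additional to the PHQ-9 of the preceding paragraph. The paragraph's opening supports this, since it says suicidality will also be assessed.
- *Literal:* the optional C-SSRS at unscheduled visits, named in the sentence immediately before.

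The broad reading is the likelier intent. The wording does not rule out the literal one. The 24-hour report is less exposed than the stop and referral, because it is tied to the event rather than to the test.

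**Step 2: whether another section closes the gap on the literal reading.**

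| Protocol section | What it requires | Mandatory stop or referral after a positive scheduled C-SSRS? |
|---|---|---|
| 10.14 | Physician confirmation before the subject leaves, for any test | No |
| 10.13 | Investigator evaluates PHQ-9 responses, which may reveal suicidal thoughts, and refers if needed | No; tied to the PHQ-9 and left to judgment |
| 7.3 | Participation may be discontinued for listed reasons; suicidality is not named | No; permissive |
| 8.4.4 | Dose interruption is allowed | No; permissive |
| 11.1.3 | A clinically significant test result can be an adverse event | No; reporting only |
| 11.1.5 | Seriousness by investigator or sponsor judgment | No; reporting only |

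So 11.1.4 is the only mandatory rule, and its trigger is the ambiguous phrase.

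**Step 3: 10.14 against the schedule.** The discretionary sentence concerns reported or suspected events, so it can be read as for-cause use on top of the schedule. But 10.14 does not mention the schedule, and 6.4, 9.1.2 to 9.1.4, 11.1.4 and Appendix 1 all require the test at every visit. Section 11.1.4 has the same fault for the PHQ-9: it makes use after screening discretionary, while 10.13 says every visit.

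**Step 4: count of tests.**

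- Scheduled post-baseline tests per subject, Visits 3 to 16: 16 − 3 + 1 = 14.
- Those at visits where drug is still dispensed (9.1.3), Visits 3 to 15: 15 − 3 + 1 = 13.
- At Visit 16 dosing is ending anyway, so the gap there concerns referral rather than the stop.

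The stop and referral cover all 14 tests on the broad reading and none on the literal one.

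**Step 5: subjects, as an illustration only.** The documents give no rate of positive tests. Assume that 0.5% to 3% of subjects have a positive scheduled test over 56 weeks.

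- All 200 subjects: 200 × 0.005 = 1, to 200 × 0.03 = 6.
- The 150 on active drug (50 mid-dose + 100 top-dose): 150 × 0.005 = 0.75, to 150 × 0.03 = 4.5.

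Under that assumption these are upper limits on the number handled differently. Only positives at sites that both read the trigger literally and keep dosing after confirmation would count.

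**The case against.** The strongest reply is that nobody would read the rule this way. An optional C-SSRS would force a stop while the identical scheduled one would not, which makes little sense. The paragraph turns from the PHQ-9 to the C-SSRS, so the natural meaning is the C-SSRS as the additional instrument. A site could also treat the physician confirmation in 10.14 as the further assessment that sets off the rule. Section 10.13 already asks the investigator at every visit to act on signs of suicidal thinking, and the PHQ-9 and C-SSRS are given together.

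Most of this stands. The intent is probably broad, and 10.13 and 10.14 are real partial safeguards. They do not replace the rule: 10.14 asks for confirmation only, and 10.13 leaves referral to judgment on a different instrument. A mandatory stop for a rare, grave event should not depend on which antecedent the reader picks.

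On 10.14, it is fair to say that no site following the visit schedule would skip the test. A reader might infer that the C-SSRS becomes optional after screening. The schedule sections and Appendix 1 do not support that.

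**Conclusion.** The point holds as a wording defect in a safety rule. On its literal reading, 11.1.4 leaves 14 scheduled post-baseline C-SSRS tests per subject without a mandatory stop or referral, 13 of them while drug is still dispensed. Section 10.14 conflicts with the schedule in how it describes testing after screening.

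The number of subjects affected is unknown and probably small. Exclusion criterion 13 removes those with past or present suicidal behavior, or ideation with some intent to act. The illustration of 1 to 6 subjects rests wholly on an assumed rate. There is no effect on the efficacy analysis, and SAP 6.7.3 still tabulates the items at every visit.

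Two stronger conclusions are not supported:

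- A reader might infer that a positive scheduled test goes unmanaged. It does not: physician confirmation is required before the subject leaves, adverse event and SAE reporting apply, and the 24-hour report is worded by event.
- A reader might infer that the stop should not wait for physician confirmation. Nothing in the protocol says so. Confirmation already happens before the subject leaves, so skipping it would gain hours at most. It would be new policy rather than a clarification, and 8.4.5 warns that abrupt topiramate withdrawal has been associated with seizures.

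**What to change.** Make these changes in the next protocol amendment, with a letter to sites:

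1. In 11.1.4, replace *this additional assessment* with *any post-baseline C-SSRS assessment, scheduled or unscheduled*.
2. In 10.14, replace the discretionary sentence with *The C-SSRS is administered at every study visit and may also be used at unscheduled visits at the investigator's discretion.*
3. In 10.14, after the confirmation sentence, add a cross-reference to the actions in 11.1.4 for any post-baseline test. Refer to 8.4.5 for how drug is stopped (every-other-day dosing for one week). Leave the confirmation step as it is.

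The cost is the amendment and the letter. There may be a few more drug discontinuations, but 7.3 and 8.4.4 encourage those subjects to stay in follow-up off drug. Sample size, significance level, data collection and the SAP do not change.
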